### 9.3. POPULATIONS FOR ANALYSES

We will use an intention to treat analysis and consider all randomised patients who present for surgery within the timeframe outlined in the exclusion criteria.

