## 5.2. EXCLUSION CRITERIA

An individual who meets any of the following criteria will be excluded from participation in this study:

1. Any patient who is found to not be iron deficient on preoperative screening
2. Any patient who is found to have hypophosphataemia, hyperparathyroidism or low Vitamin D levels on preoperative screening
3. Current use of iron supplements
4. Pregnancy or lactation
5. Known allergic reactions to components of the IV ferric carboxymaltose or oral iron supplements
6. Significant medical co-morbidity such as neuromuscular disease, severe anaemia, cardiac disease, significant respiratory disease or impairment
7. Haematological contraindication to iron therapy such as sickle cell disease or thalassaemia
8. Significant needle phobia

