## 7. STUDY INTERVENTION DISCONTINUATION AND PARTICIPANT DISCONTINUATION/WITHDRAWAL

### 7.1. DISCONTINUATION OF STUDY INTERVENTION

Discontinuation from oral or IV iron does not mean discontinuation from the study, and remaining study procedures should be completed as indicated by the study protocol. If a clinically significant finding is identified (including, but not limited to changes from baseline iron studies or haemoglobin) after enrolment, the investigator or qualified designee will determine if any change in participant management is needed. Any new clinically relevant finding will be reported as an adverse event (AE).

The data to be collected at the time of study intervention discontinuation will include the following:

- Oral iron compliance questionnaire
- Documentation of side effects or adverse reactions
- Repeat haemoglobin and iron studies to advise patient of need to continue iron therapy outside of the study

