### 7.2. PARTICIPANT DISCONTINUATION/WITHDRAWAL FROM THE STUDY

Participants are free to withdraw from participation in the study at any time upon request. An investigator may discontinue or withdraw a participant from the study for the following reasons:

- Pregnancy
- Significant study intervention non-compliance (refusal to undergo IV iron therapy)
- If any clinical adverse event (AE), laboratory abnormality, or other medical condition or situation occurs such that continued participation in the study would not be in the best interest of the participant
- If the participant meets an exclusion criterion (either newly developed or not previously recognised) that precludes further study participation
- Participant unable to receive oral or IV iron therapy at least 3 weeks preoperatively
- A patient will be discontinued from the study if they do not proceed with surgery during the required timeline from commencing iron therapy.

The reason for participant discontinuation or withdrawal from the study will be recorded on the Iron Deficiency Case Report Form (CRF). Subjects who sign the informed consent form and are randomised but do not receive the study intervention may be replaced. Subjects who sign the informed consent form, and are randomised and receive the study intervention, and subsequently withdraw, or are withdrawn or discontinued from the study, will be replaced.

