### 8.3.9. REPORTING OF PREGNANCY

If patients are found to be pregnant prior to undergoing spinal fusion surgery they will be excluded from the trial as their surgery date will be postponed until following completion of their pregnancy. If a patient is found to be pregnant from any time after their surgical date they will continue to be included in the trial and their data collected in the usual fashion.

---

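### The set labelled intention to treat is cut by an undefined surgery timeframe, and the withdrawal and replacement rules let membership depend on what happens after allocation

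*Protocol*

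**What the plan says.** Protocol Section 9.3 states that the analysis is by intention to treat and will "consider all randomised patients who present for surgery within the timeframe outlined in the exclusion criteria". Section 5.2, which opens with "An individual who meets any of the following criteria will be excluded from participation in this study", lists eight criteria. None concerns the interval to surgery.

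Section 7.2 governs leaving the study:

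- Surgery timing, mandatory and in both arms: "A patient will be discontinued from the study if they do not proceed with surgery during the required timeline from commencing iron therapy". The timeline is not specified there.
- Late treatment, at the investigator's discretion and in both arms: "Participant unable to receive oral or IV iron therapy at least 3 weeks preoperatively".
- Non-compliance, at the investigator's discretion: "Significant study intervention non-compliance (refusal to undergo IV iron therapy", with the bracket closing there. No oral counterpart is named.
- Replacement: randomised patients who never receive the intervention *may* be replaced. Those who are "randomised and receive the study intervention, and subsequently withdraw, or are withdrawn or discontinued from the study, will be replaced".

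Section 8.3.9 adds a removal that applies to both arms: "If patients are found to be pregnant prior to undergoing spinal fusion surgery they will be excluded from the trial".

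Section 7.1 points the other way for patients who stop treatment: "Discontinuation from oral or IV iron does not mean discontinuation from the study", and their remaining study procedures are to be completed.

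Sections 4.1 and 6.3 make the trial open label, with patients aware of their allocation. Section 9.2 plans 17 patients per arm.

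**The concern.** An intention-to-treat comparison is protected by randomisation because nothing that happens after allocation decides who is counted. Here two things can. The first is whether surgery falls inside a window that the protocol does not state. The second is whether a patient is withdrawn for a reason that arises after the envelope is opened.

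Three consequences follow.

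- The surgical cut-off could be settled after allocations, and even outcomes, are known.
- The one non-compliance example in Section 7.2 belongs to the IV arm, while Sections 2.2, 2.3 and 4.2 expect poor compliance with oral iron. The named rule is therefore not symmetric.
- Because replaced patients are not explicitly retained, two analysts could build different primary sets from the same trial.

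A statistical analysis plan could define the set more clearly. It could not recover a discharge haemoglobin that the trial stopped collecting because the patient had been withdrawn.

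**Working it through.** **The plan's own figures.** Section 9.2 gives p0 = 0.6875, p1 = 0.3438, z values 1.96 and 0.84, and the formula

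N = p0q0{1.96 + 0.84√(p1q1/p0q0)}² / (p1 − p0)²

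This evaluates to 14.47, stated as 14. Rounding up to 15 and allowing 10% attrition gives 15/0.90 = 16.7, so 17 per arm and 34 in total, as stated. Whether that formula suits a two-arm trial is a separate question. Here it supplies only the arm size and the planned rates. The planned effect is 68.75 − 34.38 = 34.4 points.

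**Can the set be built from the text?**

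| Section | What it contributes | What is missing |
|---|---|---|
| 9.3 | Limits the set by a surgical timeframe and refers to the exclusion criteria | The timeframe |
| 5.2 | Eight criteria | Any timeframe |
| 7.2 | Mandatory discontinuation outside a timeline; replacement | The timeline; whether originals remain in the analysis |
| 7.1 | Patients who stop iron remain in the study | How this fits with withdrawing IV refusers under 7.2 |

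It cannot. The reference from 9.3 leads nowhere, and 7.2 does not fill the gap.

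**How much can a few patients matter?** If an arm has x events in n patients, and k patients with average risk r are dropped, the arm's rate falls by

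x/n − (x − kr)/(n − k) = k(r − x/n)/(n − k)

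A negative value means that the rate rises. At 17 per arm the planned rates are closest to 6/17 for IV (0.3438 × 17 = 5.8) and 12/17 for oral (0.6875 × 17 = 11.7).

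One patient dropped:

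- From 6/17 (35.3%): an event gives 5/16 = 31.3%, a shift of 4.0 points; a non-event gives 6/16 = 37.5%, a shift of 2.2.
- From 12/17 (70.6%): an event gives 11/16 = 68.8%, a shift of 1.8; a non-event gives 12/16 = 75.0%, a shift of 4.4.

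Two IV refusers dropped from 6/17. Two is an assumption; for scale, the protocol's 10% attrition of 17 is 1.7 patients.

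| Assumed risk of the two | Remaining rate | Change in IV rate |
|---|---|---|
| 68.75% (audit rate) | (6 − 1.375)/15 = 30.8% | 4.5 points lower |
| 100% | 4/15 = 26.7% | 8.6 points lower |
| 35.3% (arm average) | 35.3% | none |
| 0% | 6/15 = 40.0% | 4.7 points higher |

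The 8.6 points are a quarter of the planned effect (8.6/34.4 = 0.25).

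**With no treatment effect.** Assume a risk of 68.75% in both arms and removal of 1 to 4 of 17 patients from the IV arm only. The spurious difference is 0 if those removed have average risk. It is 1.0 to 5.0 points if their risk is 85% and 2.0 to 9.6 points if it is 100%. It reverses sign if their risk is below average.

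**The case against.** Read alone, Section 9.3 keeps an IV refuser who presents for surgery on time. Section 7.2 only says that the investigator *may* withdraw such a patient, and it does not say that the data then leave the analysis. The pre-discharge blood count is routine (Section 8.1), so the outcome may well exist. Sections 7.1 and 7.2 are in tension rather than flat contradiction, since one concerns stopping iron and the other discretionary withdrawal from the study. Replacement is not a bias in itself if the originals are kept. Patients who never have surgery have no discharge haemoglobin, so some condition on surgery cannot be avoided. All of this stands. It narrows the defect to the undefined timing restriction under an intention-to-treat label, and to rules that permit removal without saying who is retained.

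Three stronger readings are tempting but unsupported:

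- A reader might infer that only IV refusers are withdrawn. Surgery timing, late iron, pregnancy, adverse events and newly met exclusion criteria apply to both arms. The bracketed IV refusal can be read as an example, and no passage says that an oral patient who takes nothing must stay in.
- A reader might infer that the rules favour IV iron. That depends on the risk of the patients removed, which the documents do not give, and the sign can go either way.
- A reader might infer from the schedule (randomisation at Day −35 ± 14, so as late as Day −21) that IV patients are likelier to fail the 3-week rule because they need an infusion appointment. This uses the extreme edge of one window. The rule covers both arms, oral patients must also collect from the pharmacy, and no figure supports differential loss.

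One could also take the missing timeframe to be the 3 to 5 weeks of Section 8.1. Section 2.1, however, speaks of 4 to 6 weeks being available, and neither 5.2, 7.2 nor 9.3 adopts either interval.

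**Conclusion.** The point holds in this form. The primary set carries an intention-to-treat label, is restricted by a post-randomisation condition that the protocol does not define, and is exposed to withdrawal and replacement rules that do not say who remains in the analysis. The named non-compliance example is not symmetric between arms, and allocation is known to patients.

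The size and direction of any bias cannot be derived from the documents. The illustrations rest on assumed numbers and risks of removed patients: about 2 to 4 points per patient dropped near the planned rates, and for two IV refusers anything from 8.6 points lower to 4.7 points higher. They show only that at 17 per arm a handful of removals can move the primary comparison by a noticeable fraction of the 34.4-point planned effect. Because the ambiguity governs the primary comparison and is cheap to remove, it should be corrected in the protocol before any analysis.

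**What to change.** Amend the protocol so that Sections 5.2, 7.1, 7.2 and 9.3 agree:

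- **9.3:** analyse every randomised patient who has the surgery in the arm assigned, whatever iron was taken and whatever the interval to surgery. Report by arm, with reasons, those who never have surgery. Remove the reference to a timeframe in the exclusion criteria.
- **7.2:** for the purposes of follow-up and analysis, record IV refusal, late iron and delayed surgery as treatment deviations. Keep collecting study data, including the discharge haemoglobin, in line with 7.1.
- **Replacement:** if further patients are recruited, state that the originals stay in the set.
- **Sensitivity analysis:** report the compliant, on-time patients as a per-protocol set, with compliance and timing rules written in advance and identical in form for both arms.

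The cost is a short amendment. The recruitment target need not change on this account: the 17 per arm already includes the 10% allowance. The downside is some dilution of the estimated effect from patients who did not take the assigned iron as planned, which the per-protocol analysis would help to show.

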### 9.4. STATISTICAL ANALYSES

#### 9.4.1. GENERAL APPROACH

Advise from a biostatistician will be sought prior to data analysis.

#### 9.4.2. ANALYSIS OF THE PRIMARY EFFICACY ENDPOINT(S)

Primary Endpoint: Severe anaemia at the time of discharge from hospital

Advise from a biostatistician will be sought prior to data analysis.

#### 9.4.3. ANALYSIS OF THE SECONDARY ENDPOINT(S)

Advise from a biostatistician will be sought prior to data analysis.

#### 9.4.4. SAFETY ANALYSES

This study is not powered to demonstrate safety of either oral or IV iron therapy.

#### 9.4.5. BASELINE DESCRIPTIVE STATISTICS

Advise from a biostatistician will be sought prior to data analysis.

#### 9.4.6. PLANNED INTERIM ANALYSES

Not-applicable.

#### 9.4.7. SUB-GROUP ANALYSES

Advise from a biostatistician will be sought prior to data analysis.

#### 9.4.8. TABULATION OF INDIVIDUAL PARTICIPANT DATA

Individual data will not be provided.

#### 9.4.9. EXPLORATORY ANALYSES

None

## 10. SUPPORTING DOCUMENTATION AND OPERATIONAL CONSIDERATIONS

### 10.1. REGULATORY, ETHICAL, AND STUDY OVERSIGHT CONSIDERATIONS

#### 10.1.1. INFORMED CONSENT PROCESS

##### 10.1.1.1. CONSENT/ASSENT AND OTHER INFORMATIONAL DOCUMENTS PROVIDED TO PARTICIPANTS

Consent forms describing in detail the study intervention, study procedures, and risks are given to the participant and written documentation of informed consent is required prior to starting intervention/administering study intervention. The following consent materials are submitted with this protocol:

- Patient information sheet
- Informed consent

##### 10.1.1.2. CONSENT PROCEDURES AND DOCUMENTATION

Informed consent is a process that is initiated prior to the individual's agreeing to participate in the study and continues throughout the individual's study participation. Consent forms will be Human Ethics Committee approved and the participant will be asked to read and review the document. The investigator will explain the research study to the patient and parent and answer any questions that may arise. A verbal explanation will be provided in terms suited to the patient and parent comprehension of the purposes, procedures, and potential risks of the study and of their rights as research participants. Participants will have the opportunity to carefully review the written consent form and ask questions prior to signing. The participants should have the opportunity to discuss the study with their family or surrogates or think about it prior to agreeing to participate. The patient and/or parent will sign the informed consent document prior to any procedures being done specifically for the study. Patient and parents must be informed that participation is voluntary and that they may withdraw from the study at any time, without prejudice. A copy of the informed consent document will be given to the patient for their records. The informed consent process will be conducted and documented in the source document (including the date), and the form signed, before the patient undergoes any study-specific procedures. The rights and welfare of the participants will be protected by emphasising to them that the quality of their medical care will not be adversely affected if they decline to participate in this study.

##### 10.1.2. STUDY DISCONTINUATION AND CLOSURE

This study may be temporarily suspended or prematurely terminated if there is sufficient reasonable cause. Written notification, documenting the reason for study suspension or termination, will be provided by the suspending or terminating party to study participants, investigator, funding agency, therapeutic substance committee, and human ethics committee. If the study is prematurely terminated or suspended, the Principal Investigator (PI) will promptly inform study participants, the therapeutic substance committee, and human ethics committee and will provide the reason(s) for the termination or suspension. Study participants will be contacted, as applicable, and be informed of changes to study visit schedule.

Circumstances that may warrant termination or suspension include, but are not limited to:

- Determination of unexpected, significant, or unacceptable risk to participants
- Demonstration of efficacy that would warrant stopping

- Insufficient compliance to protocol requirements
- Data that are not sufficiently complete and/or evaluable
- Determination that the primary endpoint has been met
- Determination of futility

Study may resume once concerns about safety, protocol compliance, and data quality are addressed, and satisfy the therapeutic substance committee, TGA and human ethics committee.

---

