### 9.2. SAMPLE SIZE DETERMINATION

The null hypothesis states that there is no difference between oral and IV iron therapy in the incidence of severe anaemia at the time of discharge following elective spinal fusion surgery. The primary outcome measure is the Incidence of severe anaemia (Hb <100g/L) at discharge from hospital.

Previous audit of 16 spine patients demonstrated a mean discharge Hb of 96g/L, with a standard deviation of 15.2. Haematocrit was not recorded.

Intravenous iron sucrose has been proven to increase Hb in adults with iron deficiency anaemia of various aetiologies that is non-responsive to oral iron by up to 50% (85.4g/L to 121 g/L) .

Whilst the figures for paediatric surgical patients' responsiveness to IV iron are not known (hence the development of the proposed study); it has been postulated that this may be likely to be similar to adults. Thus these preexisting findings in adults allow for an extrapolation of data to enable power calculation for the proposed study. Namely, that of the of patients being discharged with severe anaemia (Hb <10 g/dL) after spinal surgery - which currently number 68% of patients - should be able to be halved (50% decrease) through judicious and appropriate IV iron therapy.

In view of the lack of previously defined population characteristics, power calculations have been done using:

- a two study group design (Population rates of Discharge Hb<100 of 68.75% observed previously, compared to the expected post iron-infusion rates of Discharge Hb<100 of 34.38%, a figure chosen for reasons outlined above.)
- Further, while data will be collected in a continuous manner, it will be analysed as dichotomous, binomial data (two outcomes only: Hb >10 g/dL or Hb <10g/dL.) to reduce the number of patients required for the study.
- Assumption of alpha of 0.05, as per current medical research convention 
- Assumption of power (1-beta) of 0.8 as per current medical research convention 

This will result in an expected sample size of approximately 14 patients in the treatment group.

This figure has been reached using the following equation (fig. 1), which was selected to meet the above criteria . The calculation was performed using the on-line tool at <http://clincalc.com/stats/samplesize.aspx>.

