### 10.1.6.SAFETY OVERSIGHT

Safety oversight will be under the direction of the **Human Research Ethic Committee (HREC)** at the Women's and Children's Hospital. **[name], consultant paediatric anaesthetist will act as a medical monitor for this trial. All adverse effects and complications will be reported to him for review and presentation to the HREC. [name] is independent from the study conduct and free of conflict of interest.** The investigators will immediately report any serious adverse events (SAE) to the **HREC** and all adverse events (AE) will be presented at least semiannually to assess safety and efficacy data on each arm of the study.

---

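### The protocol allows stopping for efficacy and a six-monthly look at efficacy by arm, yet declares interim analyses not applicable and sets no boundary

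*Protocol*

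**What the plan says.** Four places in the protocol bear on this.

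- **Section 10.1.2** gives circumstances that may justify suspending or ending the study. They include "Demonstration of efficacy that would warrant stopping", "Determination that the primary endpoint has been met" and a finding of futility. None has a threshold, a time or a named decision-maker.
- **Section 10.1.6** (safety oversight) says that "all adverse events (AE) will be presented at least semiannually to assess safety and efficacy data on each arm of the study". The reports go through an independent medical monitor to the ethics committee.
- **Section 9.4.6**, headed "9.4.6. PLANNED INTERIM ANALYSES", consists only of the statement that it is not applicable.
- **Section 9.2** bases the sample size on "Assumption of alpha of 0.05, as per current medical research convention" and "Assumption of power (1-beta) of 0.8 as per current medical research convention", with z = 1.96 in the formula. That is one two-sided test, with no allowance for repeated looks.

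**The concern.** Nobody can show efficacy, or judge that a comparative primary endpoint has been met, before the trial ends without comparing the arms. Such a comparison is an interim analysis, which Section 9.4.6 says does not apply. A reader of Sections 10.1.2 and 10.1.6 would conclude that it may happen.

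Two things are at stake. If a review ended the trial because the difference looked significant, the 0.05 in Section 9.2 would no longer describe the chance of a false positive over the whole trial. And a trial of this size that stops early does so only on a difference larger than the one planned for, so the reported effect would tend to be too large.

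Sections 4.1 and 6.3 rely on a blinded statistician and blinded outcome assessors to limit bias. The protocol does not say who would prepare efficacy data by arm for the six-monthly review.

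**Working it through.** **1. The plan's own figure.** Inputs from Section 9.2: "Population rates of Discharge Hb<100 of 68.75% observed previously", so p0 = 0.6875; "expected post iron-infusion rates of Discharge Hb<100 of 34.38" per cent, so p1 = 0.3438; z values 1.96 and 0.84.

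N = p0q0 × {1.96 + 0.84 × √(p1q1/p0q0)}² / (p1 − p0)²

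- p0q0 = 0.6875 × 0.3125 = 0.2148; p1q1 = 0.3438 × 0.6562 = 0.2256
- bracket = 1.96 + 0.84 × 1.0247 = 2.8208
- N = 0.2148 × 2.8208² / 0.1181 = 14.47

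The protocol states 14, so the figure reproduces to within rounding. Rounding 14.47 up to 15 and dividing by 0.9 gives 16.7, hence 17 per arm. The calculation assumes a single analysis.

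**2. Possible number of looks.** The synopsis estimates 36 months, and 36/6 = 6 reviews if the last coincides with the final analysis. The 36 months include follow-up after the last primary endpoint, so fewer informative looks are likely. I use 1, 2, 3 and 6.

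**3. Type I error if every look is tested at two-sided p<0.05.** This threshold is an assumption. Large-sample theory with equally spaced looks gives about 5.0%, 8.3%, 10.7% and 15.5% for 1, 2, 3 and 6 looks.

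For this trial I computed it exactly: both arms have the same event rate, outcomes are binomial, and the probability of a first rejection is summed over the looks.

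| Looks (patients per arm) | Chi-square, rate 0.6875 | Fisher, rate 0.6875 | Chi-square, rate 0.5 | Fisher, rate 0.5 |
|---|---|---|---|---|
| 17 | 4.7% | 2.0% | 5.8% | 2.4% |
| 9, 17 | 8.5% | 3.2% | 8.9% | 3.9% |
| 6, 12, 17 | 11.8% | 3.2% | 12.5% | 4.0% |
| 3, 6, 9, 11, 14, 17 | 14.8% | 4.4% | 15.1% | 4.9% |

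Chi-square is without continuity correction. Moving the looks slightly changes little at the rate of 0.6875: 8 and 17 per arm give 8.6% and 2.9%; 6, 11 and 17 give 11.5% and 3.0%.

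**4. Overstatement.** Take a look at 9 per arm with the uncorrected chi-square. The strongest result with a three-event difference is 3 against 0: z = 0.333/√(0.1667 × 0.8333 × 2/9) = 1.90, below 1.96. With 4 against 0, z = 0.444/√(0.2222 × 0.7778 × 2/9) = 2.27. A significant result therefore needs a difference of at least 4/9 = 44 percentage points, against the planned 68.75 − 34.38 = 34.4.

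**5. Futility.** Stopping for futility can only remove chances to reject the null hypothesis. It lowers power and cannot raise the type I error.

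**The case against.** The strongest case against is that no efficacy testing is planned at all. Section 10.1.6 concerns safety, the subject of its sentence is adverse events, and the recipients are an ethics committee and a medical monitor independent of the study's conduct. Section 10.1.2 is a general list of what may justify closure, and its condition for resuming mentions only safety, compliance and data quality. On this reading the efficacy wording is left over from a template and Section 9.4.6 governs. That is plausible, and it is why the effect on the error rate is conditional. It does not resolve the conflict: the current text still names efficacy by arm and still permits an efficacy stop. A separate analysis plan would not resolve it either, because the protocol has not deferred the matter but has declared it not applicable.

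A reader might infer three stronger things that the documents do not support:

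- **That the type I error of this trial is about 15%.** That figure needs six looks, p<0.05 at each and an uncorrected chi-square, one look being at 3 patients per arm. The protocol states none of these. With Fisher's exact test, a usual choice for tables this small, the error stayed below 5% in every scenario above. That protection comes from the test's conservatism and not from any rule.
- **That the futility ground contributes to the inflation.** It does not (step 5).
- **That six-monthly efficacy data would change recruitment or transfusion decisions.** Nothing says that results by arm return to the treating team, who already know each patient's allocation and haemoglobin.

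**Conclusion.** The contradiction between Sections 9.4.6, 10.1.2 and 10.1.6 stands as a matter of text and should be corrected. The protocol permits stopping for efficacy, provides for a look at efficacy by arm, sets no boundary, and sizes the trial on a single test.

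The effect on the error rate is a range that depends on assumptions: stopping at nominal p<0.05, two to six looks, and 17 per arm at the end. At the protocol's control rate it is about 8.5% to 15% with an uncorrected chi-square and about 3% to 5% with Fisher's exact test. The supportable statement is that no rule controls the error, not that it is inflated by a known amount. The tendency of an early stop to overstate the effect follows from the small numbers. The futility ground belongs here only because it too implies an interim comparison that Section 9.4.6 excludes.

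**What to change.** **Preferred.** In Section 10.1.2, delete the efficacy and endpoint-met grounds, and the futility ground for consistency with Section 9.4.6. In Section 10.1.6, limit the six-monthly review to safety data and state that efficacy will not be compared by arm before the last patient's primary endpoint is recorded. Section 9.4.6 and the single test at 0.05 can then stand. The cost is three bullets and one phrase; safety review, visits and sample size are unchanged.

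**If an efficacy stop is wanted.** Replace the entry in Section 9.4.6 with one named look, its timing, the test, who sees the result, and a boundary that holds 5% overall. For two equally spaced analyses, large-sample values are about 0.029 at each (Pocock) or about 0.048 at the final analysis (O'Brien-Fleming); they should be checked exactly at this sample size. A very strict boundary would have almost no use: under the protocol's own assumed rates, p<0.001 at 8 to 9 per arm is reached with probability of about 0.2% to 0.8% (Fisher) or 1.5% to 3.6% (chi-square). If futility stopping is kept, its rule and its cost in power should be stated there too.
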